Finally, we employ quantitative sensory testing (QST) to quantitatively measure participants sensory and pain thresholds for mechanical stimulation, thermal stimulation, and pressure stimulation as described in detail above. *All QST will be performed by a clinician/researcher blinded to meditation and exercise intervention.* These well-validated measures provide a quantitative assessment of pain during the meditation and exercise intervention. QST pain assessment will occur at baseline (intake day) and day 29 (48 hours after the last intervention). All QST measures will occur on the forearm and in the lumbosacral area identified by the individual participant as being painful. Briefly, mechanical testing is accomplished using von Frey filaments and assesses general mechanical sensitivity and mechanical allodynia in cases of cutaneous hypersensitivity. Filaments are similar to fishing line thread and stimulus ranges from undetectable to detectable to painful. Any pain is similar to "pin prick" pain. Thermal pain is assessed using a Peltier-type device (Medoc Pathway) to measure thermal pain threshold. Similarly, we assess the qualitative nature of thermal pain by applying a 45°C constant heat stimulus to the participant's back. 45°C is the molecular activation threshold for pain receptors and allows for an analysis

of thermal allodynia using VAS scales for the sensory and emotional component of pain. Finally, we will use a manual pressure algometer (0.2-2cm diameter, Wagner Instruments) to first measure pressure pain thresholds. Threshold detection is then followed by a constant pressure stimulus at an individual participant's pain threshold to determine the sensory and emotional VAS properties of the stimulus. All of these quantitative sensory techniques are safe and carry only minor risk for participants.

Assessment - Meditation and Mindfulness

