All participants in the meditation groups will complete the Freiburg Mindfulness Inventory (FMI) at the beginning of their first day of exercise/meditation and on the last day of the trial. The FMI is a 30-item tool that assesses an individual's experience with meditation and mindfulness. For this feasibility study, data from the FMI will be particularly useful in evaluating whether there were any changes in mindfulness that developed during the trial. Failure to increase mindfulness during the trial might be a sign that a patient failed to "buy in" to the meditation intervention. We will also evaluate the likelihood of a patient to continue to meditate (or exercise) using a qualitative exit survey given on day 29. There are no safety concerns associated with the FMI or custom exit survey.

Assessment – Anxiety

To account for changes in anxiety during the current exploratory trial, we will use the State-Trait-Anxiety Inventory (STAI) form Y to evaluate state anxiety and the Fear-Avoidance Beliefs Questionnaire (FABQ) to evaluate fear avoidance behavior. Subjects will report their state anxiety (using a survey) before and after each trial. FABQ will be evaluated on day 1 and day 29. There are no serious safety concerns associated with this survey.

Assessment - Exercise

As described above, we will be using multiple assessment tools to evaluate physical fitness and exercise in this trial. General fitness will be determined by the International Physical Activity Questionnaire – Short Form (IPAQ-short) and a clearance of physical readiness for exercise will be determined by the AHA/ACSM Health/Fitness Facility Pre-participation Screening Questionnaire. Exercise exertion will be measured daily through active heart rate monitoring during exercise and the Borg Rate of Perceived Exertion (Borg RPE)⁸. Finally, throughout the 4 week trial, participants will be asked to wear wrist-based health activity monitors. These watches monitor and record activity and other factors. There are no serious safety concerns associated with these surveys or monitoring methods.

5. Sample selection

Adults with chronic low back pain who are otherwise healthy will be recruited for participation in this study. The AHA screening questionnaire will be administered during the screening process to determine whether potential subjects meet the inclusion/exclusion criteria.

Eligibility Criteria:

Inclusion criteria

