Title Page:

Statistical Analysis Plan

Combined exercise and meditation as a treatment for patients with chronic back pain

NCT number not available

12/21/17

Statistical Analysis Plan
Combined exercise and meditation as a treatment for patients with chronic back pain

This is a single-blind, single center randomized clinical trial comparing a treatment group (MedExT) versus a control group. The current analysis plan is specific to this study for reporting and publication purposes but is part of a larger study. The primary outcome of this study is to compare the post Roland-Morris Disability Questionnaire scores between the two independent groups. This will be achieved by comparing the mean post disability score for the MedExT group to the mean post disability score for the control group using a two-sample t-test (or the Mann-Whitney-Wilcoxon rank sum test if normality does not hold) in which a one-sided p-value < 0.05 will be considered a significant improvement in the MedExT group.

Three secondary treatment responses will be studied. The first will test whether the MedExT group will significantly increase mean scores on the Freiburg Mindfulness Inventory as determined by a two-sample t-test or the Rank Sum test given distributional properties of the data ($P < 0.05$). The second will explore whether the MedExT treatment will significantly influence a mean change in responses on the three psychological inventories administered; the Fear Avoidance Beliefs Questionnaire, the STAI state anxiety inventory and the STAI state trait inventory, $p < 0.02$. The third outcome measured will study mean response changes in the series of 14 Quantitative Sensory Tests measured at baseline and at the completion of the 4-week intervention period. Significant mean pre/post differences between groups will be identified using the two-sample t-test or the Rank Sum test where appropriate adjusting the significance level to 0.005. Additionally two pain outcome measures will be repeatedly observed throughout the study taken at baseline and on each intervention day. These measures are the VAS pain intensity score and the VAS pain unpleasantness. A repeated measures multivariate analysis of variance (MANOVA) procedure will be used to determine if the vector of timed responses is significantly different between the two study groups.

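### The 14 sensory tests are compared on unadjusted change scores, and the FABQ on a mean change with no test named; adjusting for the Day 1 value already collected would usually be more precise

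*SAP*

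**What the plan says.** The SAP's paragraph on secondary treatment responses sets the QST endpoint as change: "The third outcome measured will study mean response changes in the series of 14 Quantitative Sensory Tests measured at baseline" and again after the four weeks. The test follows: "Significant mean pre/post differences between groups will be identified using the two-sample t-test or the Rank Sum test where appropriate", with the authors "adjusting the significance level to 0.005".

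The psychological inventories (FABQ and two STAI scales) have a separate sentence. It asks whether treatment will "significantly influence a mean change in responses on the three psychological inventories administered" and sets a threshold of 0.02. It names no test.

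The protocol schedules the baseline values. Section 4 (Pain and Disability) puts QST at the intake visit and on Day 29. Section 4 (Anxiety) states: "FABQ will be evaluated on day 1 and day 29". Section 3 has state anxiety assessed at intake, and section 4 has it reported before and after each session. The protocol gives no schedule for a trait score.

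No model in either document includes a baseline covariate.

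**The concern.** A change score is one particular form of baseline adjustment: it subtracts the Day 1 value with a fixed coefficient of 1. The coefficient that minimises residual variance is r × SD_post / SD_pre. When that is below 1, subtracting the whole Day 1 value puts Day 1 measurement noise into the outcome. A group that happens to start more sensitive then tends to show more apparent improvement.

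There is some reason to expect r below 1 here. Filament thresholds come from a stepped series with few trials per filament, pressure thresholds from two trials per site, and VAS ratings from single three-second stimuli (protocol section 3). This is an inference, since the documents report no reliability figure.

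What is at stake is precision. QST is the outcome set that the protocol assigns to a blinded assessor, and it faces the strictest threshold in the SAP. Protocol section 6 invites only participants who complete at least 80% of sessions to the exit visit, so fewer will have Day 29 data than were randomised. Protocol section 8 also wants estimates from this study to inform a larger trial.

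**Working it through.** **Inputs from the documents.** Change is the QST endpoint, at 0.005 per test, with Day 1 and Day 29 values. Change is the FABQ endpoint, at 0.02, also with Day 1 and Day 29 values.

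**Not in the documents, so assumed.** Sample size (10 to 40 per arm), 1:1 allocation, r (0.3 to 0.95), equal SDs unless stated, and two-sided testing. The SAP states a side only for the primary outcome: "a one-sided p-value < 0.05 will be considered a significant improvement in the MedExT group". There is no power figure in the plan to reproduce.

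**Step 1: residual variance in general.**
- Change score: SD_pre² + SD_post² − 2r·SD_pre·SD_post
- Baseline-adjusted: SD_post²(1 − r²)
- Difference: (SD_pre − r·SD_post)², which is never negative.

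**Step 2: equal SDs (set to 1).** The variances are 2(1 − r) and 1 − r², so the ratio of adjusted to change is (1 + r)/2. This is 0.65 at r = 0.3, 0.75 at 0.5, 0.85 at 0.7, 0.90 at 0.8 and 0.95 at 0.9.

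**Step 3: unequal SDs.** With SD_pre = 1, SD_post = 1.3 and r = 0.9, the best slope is 0.9 × 1.3 = 1.17, so the change score corrects too little. Its variance is 1 + 1.69 − 2.34 = 0.35, against 1.69 × 0.19 = 0.32 after adjustment. Adjustment is still the more precise.

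**Step 4: power in small samples.** The change-score test uses a noncentral t with 2n − 2 df and noncentrality d/√[2(1 − r)·2/n]. The adjusted test uses 2n − 3 df and d/√[(1 − r²)·(2/n)·(1 + x)], averaged over the chance baseline imbalance x. For each r, d is set so that the change-score test has 50% power. Power after adjustment:

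| Level | n per arm | r = 0.3 | 0.5 | 0.7 | 0.8 | 0.9 | 0.95 |
|---|---|---|---|---|---|---|---|
| 0.005 | 10 | 70.7% | 62.5% | 55.2% | 52.0% | 49.0% | 47.6% |
| 0.005 | 20 | 73.3% | 65.0% | 57.6% | 54.3% | 51.2% | 49.8% |
| 0.005 | 40 | 74.2% | 66.0% | 58.6% | 55.2% | 52.1% | 50.7% |
| 0.02 | 10 | 67.8% | 60.7% | 54.6% | 51.9% | 49.4% | 48.2% |
| 0.02 | 20 | 69.8% | 62.6% | 56.4% | 53.6% | 51.1% | 49.9% |
| 0.02 | 40 | 70.5% | 63.4% | 57.2% | 54.4% | 51.8% | 50.6% |

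A simulation of 10,000 trials (20 per arm, r = 0.5, d = 1.0, level 0.005) gave 57.4% and 72.5%, against 57.6% and 72.7% from the formulas.

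**Step 5: the same gain as sample size.** By the normal approximation, n per arm for 80% power at d = 0.8 and r = 0.5 is:
- At 0.005: 2(2.807 + 0.842)²/0.64 = 41.6, so 42. After adjustment, 0.75 × 41.6 = 31.2, so 32.
- At 0.02: 2(2.326 + 0.842)²/0.64 = 31.4, so 32. After adjustment, 0.75 × 31.4 = 23.5, so 24.

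**The case against.** The strongest reply is that nothing here is an error. Under randomisation a two-sample comparison of change is unbiased and keeps its type I error, and chance baseline differences average to zero. The outcomes are secondary, the trial is exploratory, and its stated aim is feasibility. All of that stands, and it limits the point to efficiency.

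Four stronger readings are tempting, and the documents do not support them.

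- **That the change score always over-corrects.** This needs r × SD_post / SD_pre below 1. The documents give no SDs, and Step 3 shows a case that goes the other way.
- **That a minimum gain, such as five points of power, can be promised.** By the normal approximation with equal SDs and r = 0.8, 80% becomes only 84.4% at 0.02, and 20% becomes only 23.1% at 0.005. Small samples reduce the gain further.
- **That the SAP specifies a t-test or rank sum test on FABQ change.** The sentence naming those tests concerns the QSTs. For the inventories the test has to be inferred.
- **That the sensory results would be biased or falsely significant.** Neither follows from using change scores in a randomised comparison. The adherence condition on the exit visit is a separate matter, which choosing between these two analyses does not settle.

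Two practical objections also stand and shape the fix. The pressure VAS is rated twice on Day 29, at the Day 1 threshold and at the new one, so its covariate must be defined. A model on ranks gives a difference in rank units, which has no direct clinical meaning.

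**Conclusion.** The point holds as a matter of efficiency. The planned QST comparison is valid, but it makes poorer use of a baseline value the trial already collects. For the FABQ the method is also left unstated.

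The residual variance after adjustment is never larger, whatever the SDs. Its size relative to the change score depends on r, which is not given. At an assumed 20 per arm, starting from 50% power at 0.005, the gain is about 15 points at r = 0.5, 8 at 0.7, 4 at 0.8 and 1 at 0.9. It disappears or turns very slightly negative at about 10 per arm with r of 0.9 or more, where the lost degree of freedom and the imbalance term outweigh the small variance reduction.

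These figures assume equal SDs, 1:1 allocation, two-sided tests and roughly normal data. They were not worked out for the rank sum alternative. The change is worth making because it costs almost nothing, not because the planned tests would mislead.

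**What to change.** In the SAP's secondary-outcome paragraph:

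- **QST.** Analyse each test with a linear model of the Day 29 value on group plus the Day 1 value of the same measure. Report the adjusted group difference with its confidence interval.
- **Pressure VAS.** Use the Day 1 rating at threshold as the covariate for each of the two Day 29 ratings.
- **Inventories.** Name the same model for the FABQ, and for each STAI scale for which a pre-intervention score is collected, so that the 0.02 family uses one method. State which score serves as baseline.
- **Ranks.** Where ranks are needed, for example for stepped filament thresholds, fit the model to ranked Day 29 and Day 1 values for the test, and report raw change descriptively.

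The cost is a few sentences in the SAP and one extra degree of freedom per test. It needs no new data, visits or procedures.

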(e.g. if baseline trials indicated a pressure threshold of 50 N then subject will be asked to evaluate the pain of that stimulus). During final testing trial (day 29), the pressure pain threshold will be re-measured to determine if there is a change from baseline. For the quality/unpleasantness testing, subjects will be tested on day 29 at their original baseline pressure threshold (from day 1) AND the new threshold determined day 29. This will allow an analysis of change from baseline and pain at threshold across the experiment.

Following baseline pain testing, subjects (in the exercise only and meditation then exercise groups) will be set-up for training on the exercise protocol. Subjects will become familiarized with the exercise protocol, including the physiological measures to be assessed [heart rate (HR)], the Borg Rate of Perceived Exertion (RPE) Scale, and the treadmill speed at which they will be walking. Subjects will be instructed to step up onto the treadmill and stand on the sides not the belt or belt deck. The researcher will slowly raise the speed to 2 mph. The subject will be instructed to step on the treadmill at this time. After 30 seconds, the speed will be ramped up to 2.5 mph and after another 30 seconds, the speed will be ramped up to their prescribed session speed (± 3.5 mph). They will also be instructed to walk with a natural gait pattern, allowing bilateral arm swing. To allow a natural arm swing, subjects are unable to hold onto the treadmill arm rails. Subjects will be introduced to the Borg RPE scale and asked to provide subjective feedback on their level of exertion at the initiation of and during the final minute of this 5 minute training period (Borg).

Intervention Sessions

Subjects will be scheduled for 20 intervention sessions during their time in the study – that is five sessions per week over four weeks. Subjects are only required to return to campus for the first session of each week. The remaining four weekly sessions can be completed at home on a personal treadmill or in the community, such as a local gym. Subjects are able to complete all sessions at Duquesne University if that is their preference. Sessions will be scheduled/encouraged to occur at the same approximate time each day to control for factors that may influence exercise performance and assessments.

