Assessments in this exploratory trial are designed to evaluate four elements of the trial: (1) Pain and Disability, (2) Meditation, (3) Anxiety and Stress, and (4) Fitness and General Health and. Although these elements are not mutually exclusive and multiple survey tools overlap, we describe these elements as individual groups of assessments below for ease of interpretation. General assessment includes demographic information (gender, age, race/ethnicity, and education level) and handedness. The primary outcome of this trial is a reduction in disability as measured by the RMDQ (see below). See Appendix 1 – Instruments for all surveys and questionnaires.

Protocol Pain and Disability

There are multiple assessments for experimental measurement of pain. First, we will use the Roland-Morris Disability Questionnaire, which provide a qualitative analysis of the disability that is associated with an individual's chronic low back pain. This is our primary outcome for the trial. We hypothesize that exercise, meditation, and combined exercise/meditation will decrease disability in patients. Second, we will use standard visual analog scoring of instantaneous back pain for participants before and after exercise (or meditation in the "meditation only" control group or audio book in the negative control group) during each day of the trial. These scales will be included in the subject online diary (Qualtrics Survey Platform) for participants completing "at home" trials.

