Compensation for participation in this study is based on the number of sessions completed. Compensation for the intake session and each completed intervention session is \$4.50 and compensation for the Exit Session is \$100. Therefore, if a participant completes this project in its entirety (intake session, 20 intervention sessions, and the Exit session), they will receive \$200. Only participants who complete at least 80% of all intervention sessions (greater than 16 of 20 sessions) and the intake session, will be invited to complete the Exit Session. If the subject chooses to withdraw before completing at least 80% of the intervention sessions, they will receive partial compensation for the sessions that they have completed.

As part of this study, we are also interested in identifying barriers to participant interest and persistent. To identify these barriers, we will utilize an anonymous online survey of participants who drop out of the study. If a participant consents to the Duquesne study but later drops out of the study, they will be directly given a URL for a survey.

7. Informed consent procedures for exercise/meditation study

As noted above, initial consent is obtained through the University of Pittsburgh Department of Physical Meditation and Rehabilitation Research Registry (PMR3) (Pitt IRB # PRO12030122). This consent is obtained by UPMC/Pitt Physician [name] (co-I), and his partners, Drs. [name], [name], and [name] (see *Support Letter*) along with Physical Medicine and Rehabilitation Clinical Research Coordinator [name], MS. Backup recruitment efforts will occur in collaboration with the CTSI (see *Support Letter*) using the Pitt + Me registry. IRB approved consent is provided when patients are entered into the Pitt + Me registry.

Subsequent consent for the exercise/meditation study here at Duquesne occurs as follows:

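### The repeated-measures MANOVA of the daily VAS scores, run in the standard way, drops anyone with one missed score, although the protocol tolerates 3-4 missed sessions; the SAP also leaves its alpha and deciding effect open.

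*SAP*

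**What the plan says.** After the primary outcome and three secondary responses, the SAP adds that "two pain outcome measures will be repeatedly observed throughout the study taken at baseline and on each intervention day". These are VAS pain intensity and VAS pain unpleasantness. The two groups are compared on them as follows: "A repeated measures multivariate analysis of variance (MANOVA) procedure will be used to determine if the vector of timed responses is significantly different". The SAP gives a significance level for the RMDQ (0.05, one-sided), the mindfulness inventory (0.05), the psychological inventories (0.02) and the sensory tests (0.005), but none for this test. Neither document has an analysis rule for missing VAS scores.

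The Protocol supplies the context:

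- Section 3, Intervention Sessions: "Subjects will be scheduled for 20 intervention sessions during their time in the study". Only the first session of each week must be on campus: "The remaining four weekly sessions can be completed at home on a personal treadmill or in the community".
- Section 4, Pain and Disability: the daily measure is "standard visual analog scoring of instantaneous back pain for participants before and after exercise", or before and after the corresponding control activity. For off-site days, "These scales will be included in the subject online diary".
- Section 6, compensation: "Only participants who complete at least 80% of all intervention sessions (greater than 16 of 20 sessions") and the intake session are invited to the Exit Session.
- Section 6 also plans a survey for use "If a participant consents to the Duquesne study but later drops out of the study". Section 8 promises to report withdrawal percentages and adherence to the daily measurements.

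**The concern.** A repeated-measures MANOVA works on a full response vector for each person. Unless told otherwise, standard software removes anyone with a gap, whichever effect is tested. Here the vector is long, most entries may be self-recorded away from the site, and the trial's own adherence rule accepts missed sessions. The analysis set for the daily pain scores could thus be much smaller than the set the trial regards as adherent, and made up of its most diligent members. Two things are at stake: power, and bias if people skip sessions or diary entries when their pain is worse (or better).

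There is also an open choice. A repeated-measures MANOVA typically reports a group effect, a group-by-time effect and, if requested, an omnibus comparison of the mean vectors. With no alpha and no statement of which decides, the choice could be made after seeing the data. The same holds for the before-session and after-session readings.

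**Working it through.** **Length of the vector.** Protocol section 3 gives 5 sessions × 4 weeks = 20, which matches its stated total of 20. Adding baseline: 20 + 1 = 21 scores per scale, a minimum if one reading per day is used. (The section's list of optional off-site days leaves out days 17-20 and needs reconciling with the session total, but the text states 20 intervention days twice.)

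**Misses tolerated.** 80% of 20 is 16, so one half of the Exit Session rule allows 4 misses. More than 16 means 17 or more, so the other half allows 3. The two halves disagree and must be reconciled. Off-site sessions: 4 × 4 = 16 of 20.

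**Completeness.** The documents give no completion rate, so q (daily completion) is assumed, with baseline always present. Independent misses: P(all 20) = q^20. Misses clustered within person, correlation 0.2: beta-binomial with a = 4q and b = 4(1 − q), since 1/0.2 − 1 = 4.

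| q | all 20, independent | all 20, clustered | ≥17 sessions, independent | ≥17 sessions, clustered |
|---|---|---|---|---|
| 0.90 | 12% | 46% | 87% | 79% |
| 0.95 | 36% | 68% | 98% | 90% |
| 0.98 | 67% | 86% | 99.9% | 96% |

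Not everyone lost is adherent. At 95% with clustered misses, 32% lack a full vector: about 22% have 17-19 sessions and about 10% have 16 or fewer. At 98% the split is about 10% and 4%.

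**Power.** All inputs are assumed: 30 randomised per arm, two-sided 0.05, equal correlation 0.5 between days, and a group difference either constant at 0.5 SD or rising by 0.04 SD per day to 0.8 SD. Holding the test fixed (baseline-adjusted average of the daily scores), so that only the discarding of participants differs, simulation gives:

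| Misses | All available scores, constant / rising | Complete cases only, constant / rising |
|---|---|---|
| 95%, clustered | 96% / 86% | 83% / 69% |
| 95%, independent | 95% / 85% | 50% / 38% |
| 98%, clustered | 94% / 86% | 90% / 80% |

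The Monte Carlo error is at most 1.1 points. The adjusted average is not the SAP's test. For two readings of the SAP's own test, going from no missing data to complete cases at 95% clustered:

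- one-degree-of-freedom group effect: 71% to 54% (constant), 56% to 41% (rising);
- whole-vector test: 37% to 20% (constant), 93% to 59% (rising).

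The whole-vector test also cannot be computed with fewer than 21 + 2 = 23 complete participants.

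**Bias.** In one simulated scenario the odds of a miss double per SD of last recorded pain, 5.4% of scores are missed and the true effect is 0.50 SD. The complete-case estimate averages 0.455 and a mixed model 0.505. The distortion is modest, and the scenario satisfies the mixed model's own missing-at-random assumption.

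**The case against.** The strongest reply has four parts.

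- **The SAP does name a test.** A reader might infer that no tested effect is stated. That goes too far: the SAP names a between-group comparison of the vector of scores, most naturally an omnibus one. What stays open is narrower: whether that, the group effect or group-by-time decides, at what alpha, and on which reading.
- **Listwise deletion is not written down.** True: it is how the named procedure normally runs. But the SAP offers no alternative, so the default would govern.
- **The size is assumed throughout.** This stands. The share with complete scores runs from 12% to 86% over plausible inputs, and at 98% completion with clustered misses the power loss is only 4-6 points. The direction follows from the documents; the size does not.
- **The stakes are limited.** The VAS scores come after the primary and the three secondary responses in a study that the Protocol frames as a feasibility trial, and section 8 would make incompleteness visible. Visible is not analysed, however, and these are the trial's only daily back-pain scores.

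A reader might also infer that the whole-vector test is always weak. It is not: with complete data and the rising effect it has 93% power, against 86% for the baseline-adjusted average.

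**Conclusion.** The concern holds as a cheap improvement. The mismatch needs no assumed number: someone with 17-19 of 20 sessions is adherent by the Protocol's rule and, under a standard MANOVA, is dropped from the VAS comparison. This lowers power under every reading of the test and can bias the comparison if misses depend on pain.

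How much is lost cannot be derived from the documents. At an assumed 95% completion and 30 per arm, the loss is roughly 12-17 points for clustered misses and 45-47 for independent misses on a fixed test; it is small at 98% clustered. These figures pool adherent participants with those who withdraw, so they should not be read as the loss among adherent participants alone.

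The missing alpha, deciding effect and choice of reading are separate gaps that stand regardless of completion. Nothing here touches the primary RMDQ comparison.

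**What to change.** For each VAS scale, replace the MANOVA with a linear mixed model on all available daily scores from all randomised participants in the two groups, with group, day, group × day and baseline VAS. Pre-specify:

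- one deciding group contrast per scale, for example the difference averaged over the intervention period, with a confidence interval;
- which reading is analysed, before or after the session;
- the alpha across the two scales.

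The covariance structure and small-sample degrees-of-freedom method are for the trial statistician to choose and write down in advance. The two forms of the 80% rule in Protocol section 6 should be reconciled.

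The cost is SAP wording and slightly more modelling; no extra data are needed. There are three downsides. The model assumes data missing at random. An averaged contrast is less sensitive to some time-varying effects (the 86% against 93% above). Splitting alpha to 0.025 per scale costs about 4-8 points at 30 per arm with no missing data: 95% to 91% for the constant effect and 86% to 79% for the rising one, under the same assumed inputs.

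### The SAP's VAS analysis appears to treat the baseline score as a response, plans no baseline adjustment and names no tested effect, which costs precision and interpretability

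*SAP*

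**What the plan says.** The SAP describes a "randomized clinical trial comparing a treatment group (MedExT) versus a control group". After the primary outcome and three secondary responses, it adds a repeated-measures analysis: "Additionally two pain outcome measures will be repeatedly observed throughout the study taken at baseline and on each intervention day". It continues: "These measures are the VAS pain intensity score and the VAS pain unpleasantness". On method it says "A repeated measures multivariate analysis of variance (MANOVA) procedure will be used", the purpose being "to determine if the vector of timed responses is significantly different between the two study groups".

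No covariate is named for this analysis. No significance level or sidedness is given for it, and the SAP does not say which MANOVA effect decides the question. The closing paragraph of the SAP lists variables to be compared between groups; baseline VAS is not among them.

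The protocol supplies the number of days. Under Intervention Sessions in section 3: "Subjects will be scheduled for 20 intervention sessions during their time in the study". Under Instruments (section 4, pain and disability) it describes "standard visual analog scoring of instantaneous back pain for participants before and after exercise" on each day, so there are two readings per session, and the SAP does not say which one enters the vector.

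**The concern.** A score taken before treatment cannot respond to it, and in a randomised comparison its expected group difference is zero. Its proper use is to explain variation between patients in the later scores. If it is one more response and nothing is adjusted for it, that variation stays in the error term of any comparison of average pain level.

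The unnamed effect matters as much. A repeated-measures MANOVA yields at least three group tests: the average level, group-by-time, and the whole vector. They answer different questions and have very different power. None, as described, gives an estimated treatment difference with an interval. Section 8 of the protocol wants effect sizes to inform a larger trial, and these are the SAP's only repeatedly measured clinical pain outcomes.

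**Working it through.** **Inputs.** From the documents: 20 intervention days, hence 21 scores per scale with baseline; two randomised groups. Neither document gives a sample size, SD, correlation or effect size for this analysis, so there is no stated figure to reproduce. Assumed: equal allocation, unit variance, two-sided 0.05, equal correlation r between any two scores (compound symmetry), and an effect d that is constant over the 20 days unless stated otherwise.

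**1. Group-average test.**
- Mean of 21 scores: effect 20d/21 (a 4.8% dilution), variance (1 + 20r)/21.
- Mean of 20 daily scores, unadjusted: effect d, variance (1 + 19r)/20.
- Mean of 20 daily scores, baseline-adjusted: effect d, variance (1 + 19r)/20 − r².

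At r = 0.5 the variances are 0.524, 0.525 and 0.275. The sample-size ratio, adjusted mean against the 21-score average, is (1/0.275) ÷ ((20/21)²/0.524) = 2.1. An 80% power noncentrality of 2.80 becomes 2.80/√2.1 = 1.93, and Φ(1.93 − 1.96) = 0.49. In the same way:

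| r | Adjusted mean | Baseline dropped, no adjustment | Baseline among responses | Sample-size ratio, first against last |
|---|---|---|---|---|
| 0.3 | 80% | 67% | 63% | 1.5 |
| 0.5 | 80% | 53% | 49% | 2.1 |
| 0.7 | 80% | 35% | 32% | 3.5 |

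The last step, from dropping baseline to including it as a response, costs 3 to 4 points. The larger step is the missing adjustment. If correlation instead decays as 0.8 to the power of the lag, the three figures are 80%, 75% and 73%, so the gain depends on the correlation pattern.

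**2. Whole-vector test (Hotelling T² on 21 scores, F on 21 and N − 22 df).** Take r = 0.5 and set d so that the adjusted mean has 80% power (noncentrality 8.28 at an assumed 20 per group). The 21-score vector has the same noncentrality, so nothing is diluted, but it is spread over 21 df:
- 20 per group: 16.9%; with baseline as covariate and the 20 days kept as a vector, 17.5%.
- 40 per group: 23.8%, against 24.6%.

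Moving baseline therefore changes this test by less than one point. The loss comes from the degrees of freedom.

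**3. All tests in one case: 20 per group, mean effect 0.6 SD, r = 0.5.** Let μ be the 21 group differences, with zero at baseline. The whole-vector noncentrality is (n/2)/(1 − r) × [Σμ² − r(Σμ)²/(1 + 20r)]. For group-by-time it is (n/2)/(1 − r) × [Σμ² − (Σμ)²/21], on 20 and N − 21 df. Here (n/2)/(1 − r) = 20 and Σμ = 12.
- Constant effect, Σμ² = 7.2: whole vector 20 × (7.2 − 6.545) = 13.1, power 0.26; group-by-time 20 × (7.2 − 6.857) = 6.9, power 0.15.
- Effect growing linearly to the same mean, Σμ² = 9.371: group-by-time 20 × (9.371 − 6.857) = 50.3, power 0.90; whole vector 20 × (9.371 − 6.545) = 56.5, power 0.92.
- Adjusted mean, either shape: 10 × 0.36/0.275 = 13.1 on 1 df, power 0.94. The average including baseline has 0.68; the average with baseline dropped and no adjustment has 0.72.

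**4. Type I error.** In 20,000 simulated null trials (20 per group, r = 0.5), the whole-vector test rejected 4.9% of the time and the 21-score average 5.2%.

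**The case against.** Four objections deserve an answer.

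- **The SAP never states that baseline is in the vector.** It says only that the measures are "taken at baseline and on each intervention day" and later refers to timed responses. This is correct. Inclusion is the natural reading, not an explicit statement, and the firmer criticism is that baseline's role and the tested effect are both undefined.
- **Group-by-time uses baseline properly.** This stands: baseline is the reference for change and nothing is diluted. But that test is weak for a constant effect (0.15), so leaving the choice open is not harmless.
- **One averaged contrast asks a different question from a profile test.** It does, and that is a real change. It is justified by the estimate it provides, and the profile can be kept as support.
- **The analysis is peripheral.** It is introduced after the three secondary responses in a feasibility trial, which limits the weight of the point but not its truth.

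Two stronger readings are tempting and should be resisted. A reader might infer that the test is invalid because a chance baseline difference could make the groups look different. Under randomisation such differences are already inside the nominal error rate, as step 4 shows. A reader might also infer that placing baseline among the responses causes the large power loss. It accounts for 4.8% of the effect in the average-level test and none of the noncentrality in the whole-vector test.

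**Conclusion.** The point holds as one of precision and interpretability in a non-primary analysis. As written, the plan makes no adjustment for a baseline that it already collects, and it rests on an omnibus result whose meaning is not fixed.

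The size depends on which effect is tested. For the group average, 80% power falls to between 63% and 32% over r = 0.3 to 0.7, mostly through failure to adjust; under decaying correlation it falls only to 73%. For the whole vector with a constant effect, it falls to about 17% at 20 per group because of the 21 df. For group-by-time, power is 0.15 against 0.94 with a constant effect, and 0.90 against 0.94 with a linearly growing one. So the omnibus tests lose little when the effect builds up over the four weeks and a great deal when it does not.

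All these figures rest on the assumed sample sizes, effect sizes, correlations and 0.05 level, none of which the documents give for this analysis.

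**What to change.** For each VAS scale, make the intervention-day scores the response, the baseline score a covariate and group the factor. Name one treatment contrast: the baseline-adjusted group difference in the mean of the daily scores, reported with its 95% interval. State the significance level and sidedness, and which daily reading (before or after the session) is used. Keep the group-by-day profile or its test as supportive.

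The cost is SAP wording, since baseline VAS is already to be collected. The small downside is that the omnibus profile test is no longer the headline VAS result.
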